6.0 Study Interventions*

6.1 Description: The Garmin VivoSmart 4 (or later) physical activity tracker is worn like a watch on the user. The tracker assesses several physical states (i.e., HRV, sleep, and activity) to provide the participants with a “Body Battery” measure. This measure indicates either when the body is at optimal time for activity, or if the individual needs to rest. The tracker also monitors stress levels using heart rate variability (HRV) and provides a reminder alert to “*Take a moment to breathe.*” The tracker utilizes behavioral principles to set goals with participants based on previously completed activity. To meet these goals the tracker alerts participants after a period of inactivity, encourages regular movement throughout the day, and decreases the amount of time spent sedentary.

6.2 Behavioral Intervention: The Garmin VivoSmart 4 (or later) physical activity tracker will be part of a behavioral intervention with accepted standard of care that will help improve activity behaviors and decrease stress. This is done by prompting the participant to engage in activity when sedentary and/or stressed.

6.3 Drugs, Biologics, or Devices:

Drug/Biologic/Device Name	Describe how the article is being used under current FDA approved labeling
Garmin VivoSmart 4 (or later)	This device will be continually used to monitor participants activity and sleep.
Garmin Connect App	This app will be used by the diabetes team interventionists to monitor the data collected via the device.

6.4 Device Handling: The trackers will be kept securely locked up in the office of the investigator. No one will have access to the trackers besides those involved in this study. An inventory log will be kept of all tracker serial numbers and which tracker is sent to each participant. The tracker will be shipped to the participant after they verbally consent to the protocol and have their eligibility confirmed by the study team. Participants will activate the tracker and Garmin app upon receipt of the tracker. If the participant experiences any issues with tracker activation or use, additional study visits will be scheduled at Visit 2, Visit 3 and Visit 4 (approximately Day 14, 28, or 52). If the device is broken, the study team will schedule a virtual session to troubleshoot any issues per study calendar. If issues cannot be fixed, the participant will be offered a prepaid envelope to return the device. The study team will replace lost/ broken devices twice while the patient remains on study (during the 365 ± 30 days from enrollment). If the device is broken/lost a third time, we will evaluate if the patient should be taken off study, if the circumstances appeared to be out of the participant's control we will offer to let them stay on the study and replace the Garmin again.

PARTICIPANT MANAGEMENT

7.0 Inclusion and Exclusion Criteria*

7.1 Inclusion Criteria

- Participants aged 8-21 years of age and/or parent of participant aged 8-17 years of age
- Participants diagnosed with T1D greater than 6 months ago
- Participants must be patients at the Children's Mercy Kansas City network

7.2 Exclusion Criteria

- Participants who do not meet age criteria above
- Participants who do not have T1D
- Participants who are unwilling to wear the device for at least 6 months

7.3 Equitable Selection:

Participants will be accrued to the study from the patient population at Children's Mercy. No participant will be excluded based on sex, race, or ethnicity. However, if a non-English speaking participant speaks a language not supported by the Garmin device, they will not be able to participate.

7.4 Vulnerable Populations: *Check any vulnerable populations that are being*

targeted for enrollment into the study: (Members of the following populations may not be included as participants in the research unless selected here.)

 Children/Minors (under 7 years of age)	 CM Employees
 Children/Minors (7-17 years of age)	 CM Students/Residents/ Fellows
 Neonates (infants less than 30 days old)	 Economically or Educationally
 Neonates of Uncertain Viability (infants less than 30 days old)	Disadvantaged Persons
 Non-Viable Neonates (infants less than 30 days old)	 Prisoners
 Wards of the State	
 Fetuses	
 Pregnant Women	
 Adults with impaired decision-making capacity	

Children under age 18 are a vulnerable population. Because children recruited for this trial will be between 8 and 21 Y.O., adult parents will provide verbal consent for their child's participation who are <18 Y.O.

If a child participant reaches the age of majority (18 years old) during the study, he/she will be asked to again provide verbal consent if they wish to remain on the study.

8.0 Local Number of Participants

We will pre-screen up to 1000 participants, depending on the patients coming to the diabetes clinic. If patients meet the requirements for the study, they will be sent the information letter.

	Group 1: Pre-screening/screen failures	Group 2: participant	Group 3: parent of participant	Totals

SHORT TITLE:

Enrollment Goal: Number of participants to be enrolled = the number of participants to be consented	1000	200	100	1000 pre-screened for a total enrollment goal of 300
----------------------------------------------------------------------------------------------------------------------	------	-----	-----	------------------------------------------------------

9.0 Screening and Recruitment Methods*

9.1 Identification of Potential Participants:

How will participants be identified? (Check all that apply)

- Chart reviews
- By their treating physician who will then provide the study team's contact information to the potential participant/family
- By their treating physician who will obtain patient/family permission to share contact information with the study team
- Self-refer in response to IRB approved advertisements or websites
- Through Cerner or other CM sources (e.g. databases, billing records, pathology reports, admission logs, etc.) May involve access of records by individuals not involved in the patient's care.
- List of candidates provided through the Data Report Request Form
- Registry of individuals interested in research opportunities
- Past participant list
- Participants will roll-over from another research study: Study #
- Other:

9.2 Pre-Screening prior to HIPAA Authorization

Will any of the identification methods checked above involve access to Protected Health Information (PHI) prior to obtaining HIPAA Authorization?

- Yes

SHORT TITLE:

No

- *If yes, a “Partial Waiver of HIPAA Authorization” is required. Be sure to make this selection in the “HIPAA & Confidentiality” section below and complete [Addendum E: Waiver/Alteration of HIPAA Authorization](#)*

9.3 Recruitment of Potential Participants:

Participants will be recruited from the CMH diabetes clinic, at diabetes events CM participates in (such as T1D walks or camps), by identifying youth 8-21 Y.O. with T1D who have a predicted rise in HbA1c of 0.3 points, by CM approved electronic communication (emails or texts- including the Health Device Portal Messaging) or by physician referral to the study. Flyers describing the study generally (discussing who researchers are looking for, what they would have to do, and receiving the Garmin devices) will be posted in the diabetes clinic, CM study lists (I.e. Find a Study, the clinic intake form), and at T1D events. Also, the flyer/ link to the flyer can be sent to T1D patients via email (via CM approved email servers)/ text (CM approved SMS servers including the Health Device portal messaging). The flyers will contain the study coordinator and PI contact information so the participant can reach out for information/ screening. After the initial screening to confirm eligibility, participants will be contacted via telephone and asked if they want to be emailed the consent letter to obtain verbal consent. Participants will be called up to three times, and all visits will be virtual unless a participant requests to be in person, if so the study visit will be coordinated with their standard of care clinical visit.

10.0 Surveys and Psychometric Testing:

Participants will be administered the International Physical Activity Questionnaire (IPAQ) to measure the amount and type of physical activity each participant reports per a usual week (or last week in the short form). The Hypoglycemic Fear Scale II (HFS-II) measures attitudes and fears of diabetics towards episodes of hypoglycemia. There will be two HFS surveys used for diabetics- the Child Hypoglycemic Fear Scale (C-HFS) for participants 11-18 Y.O., and the Hypoglycemic Fear Scale for Adults >18 Y.O. The Hypoglycemic Fear Scale for Parents (HFS-P) measures the fears and actions taken by parents of children with T1D concerning hypoglycemic episodes. All surveys have been used in multiple T1D studies previously.

At the mid-point of the study (day 180) participants will be asked to complete a REDCap survey. The survey will provide the current information letter and ask if they have any follow-up questions about the study.

SHORT TITLE:

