Primary Objectives	
Measure physical activity and sleep for up to 365 days using a Garmin physical activity tracker among youth and young adults with T1D.
 
Evaluate the impact of physical activity and sleep related variables on rate of DKA admission over 90 and 180, and 365 ± 30 days
 
Evaluate the impact of physical activity and sleep related variables on change in Time in Range (TIR) and other continuous glucose monitor-derived metrics of glycemic control over 90, 180, and 365 ± 30 days
 
Test the impact of physical activity and sleep related variables on machine learning models to predict change in HbA1c, DKA admissions, and change in Time in Range over 90, 180, and 365 ± 30 days

Secondary Objectives	
Examine for correlations between self-reported physical activity (IPAQ), hypoglycemia fear (HFS-II), and parent hypoglycemia fear (HFS-P) at 0, 6, and 12 months after study enrollment.
 
Evaluate any change in physical activity levels via self-report with the IPAQ survey (to allow comparisons to external cohorts).
 
Evaluate any change in how participants feel about episodes of hypoglycemia while wearing the Garmin physical activity tracker via the Hypoglycemic Fear Scale II (HFS-II)
 
Evaluate any change in how parents feel about episodes of hypoglycemia in their children wearing the Garmin physical activity tracker via the Hypoglycemic Fear Scale II for Parents (HFS-P)

Research Intervention(s)/	Garmin physical activity tracker

Investigational Agent(s)	
IND/IDE #	NA
Study Population	Youth (8-21 YO) diagnosed with T1D and parents of youth (8-17 YO)
Sample Size	1000 pre-screened for total enrollment goal of 300 (200 youth 100 parents)
Study Duration for Individual Participants	365 Days (\pm 30 days)
Study Specific Abbreviations/ Definitions	T1D = Type 1 diabetes DKA= Diabetic Ketoacidosis IPAQ=International Physical Activity Questionnaire HFS-II=Hypoglycemic Fear Scale II HFS-P= Hypoglycemic Fear Scale II for Parents HbA1c= Hemoglobin A1c

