2.0 Objectives*

2.1 Primary Objectives:

1. Measure physical activity and sleep for up to 365 (\pm 30 days) days using a Garmin physical activity tracker among youth and young adults with T1D.
2. Evaluate the impact of physical activity and sleep related variables on rate of DKA admission over 90 and 180, and 365 \pm 30 days
3. Evaluate the impact of physical activity and sleep related variables on change in Time in Range and other continuous glucose monitor-derived metrics of glycemic control over 90, 180, and 365 \pm 30 days
4. Test the impact of physical activity and sleep related variables on machine learning models to predict change in HbA1c, DKA admissions, and change in Time in Range over 90, 180 and 365 \pm 30 days

2.2 Secondary Objectives:

1. Examine for correlations between self-reported physical activity (IPAQ), hypoglycemia fear (HFS-II), and parent hypoglycemia fear (HFS-P) at 0, 6, and 12 months after study enrollment.
2. Evaluate any change in physical activity levels via self-report with the IPAQ survey (to allow comparisons to external cohorts).
3. Evaluate any change in how participants feel about episodes of hypoglycemia while wearing the Garmin physical activity tracker via the Hypoglycemic Fear Scale II (HFS-II)
4. Evaluate any change in how parents feel about episodes of hypoglycemia in their children wearing the Garmin physical activity tracker via the Hypoglycemic Fear Scale II for Parents (HFS-P)

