4.0 Study Endpoints

1. Minutes/day of Moderate-to-vigorous physical activity (MVPA) – from Garmin device over 30, 90, 180, and 365 ± 30 days
2. Sleep minutes/day – derived from Garmin device over 30, 90, 180, and 365 ± 30 days
3. Other activity metrics derived from Garmin device over 30, 90, 180, and 365 ± 30 days
4. HbA1c – collected from Electronic Medical Record, obtained via standard care (binned as 46-135 days, 136-225 days, 226-305 days, and 306-410 days)
5. Hospital admissions for DKA (0-180 days and $181-365 \pm 30$ days)
6. 14-day Time in Range and other CGM-derived metrics of the quality of glycemic control over 30, 90, 180, and 365 ± 30 days
7. Model performance characteristics (e.g. precision, recall, F1) of predictive models for the outcomes listed in 4.1-4.6

5.0 Study Design*Participants with T1D treated at the Children's Mercy Endocrine clinic aged 8-21 years old will be asked to wear a Garmin VivoSmart 4 (or later) physical activity tracker for at least 6 months. This tracker will collect detailed physical activity and sleep data as measured by moderate to vigorous physical activity (MVPA) and sleep minutes/day. The tracker collects heart rate and accelerometry data, collected into the Garmin Connect application. The diabetes center will use the Garmin Health API connection developed by Children's Mercy Research Informatics to extract the data into a data warehouse in Microsoft Azure (CMH account). As noted in previous studies, MVPA is automatically measured by the tracker when the wearer runs for >1 minute or walks for >10 consecutive minutes. The weekly MVPA and step count are both weighted by multiplying the mean of weekday activity by 5, adding it to the mean of weekend activity and dividing the sum by 7.

$$\text{Weighted MVPA} = \frac{[(\text{MVPA}) \times 5] + (\text{MWVPA})}{7}$$

$$\text{Weighted step count} = \frac{[(\text{MSC}) \times 5] + (\text{MSC weekend})}{7}$$

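### Recruiting an unstated share of youth on a predicted HbA1c rise shifts the case mix for Objective 4, so recall and F1 for the HbA1c models will not carry over to the clinic

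*Combined protocol and SAP*

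**What the plan says.** Section 9.3 lists several recruitment routes. One is to recruit "by identifying youth 8-21 Y.O. with T1D who have a predicted rise in HbA1c of 0.3 points". The others are the diabetes clinic, diabetes events, electronic messages, "or by physician referral to the study". A predicted rise is not an eligibility criterion: section 7.1 asks only for age, membership of the hospital network and a minimum time since diagnosis ("Participants diagnosed with T1D greater than 6 months ago"). Flagged and unflagged youth will therefore be mixed. Sections 1 and 8 set the target at 200 youth, with no split by route and no cap on any route.

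Primary Objective 4 (section 2.1) is to "Test the impact of physical activity and sleep related variables on machine learning models to predict change in HbA1c", among other outcomes. Endpoint 7 (section 4.0) is "Model performance characteristics (e.g. precision, recall, F1) of predictive models".

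The plan does not name the model behind the predicted rise, its horizon or its accuracy, nor a comparator model without Garmin data. Section 26 does not list recruitment route or predicted value among the data collected. The only analysis text available, section 28.1, covers propensity matching. Its seven matching variables include baseline HbA1c and time in range, but neither route nor predicted change.

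**The concern.** The quantity used to pick some participants is a prediction of the quantity that Objective 4 sets out to predict. Recall and F1 depend on how many participants sit above a decision cut and how many truly rise. Loading the sample with youth already predicted to rise moves both, by an amount fixed by a recruitment share that the plan leaves open.

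At stake is what a primary objective can conclude. A reader of the results would take recall and F1 as a description of how the model would perform in the clinic, when part of the figure reflects who was invited. If route and predicted value are not recorded at enrolment, this would be hard to repair afterwards. How much better a model looks with Garmin data than without could also shift, but the direction depends on the share.

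**Working it through.** The plan gives no performance target, model accuracy or sample size calculation, so there is no figure to reproduce. What follows shows direction and range under stated assumptions.

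**Inputs from the documents.** Predicted rise of 0.3 points (9.3); 200 youth (1, 8); precision, recall and F1 (4.0).

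**Assumptions, not in the documents.** The route selects a predicted change P of 0.3 or more. Actual change has mean 0.1 and SD s = 0.8, 1.0 or 1.2. P explains R² = 0.20 of its variance (0.10 to 0.40 as a range). An event is an actual rise of 0.3 or more. A share f of the sample comes by this route, and the rest are unselected. Garmin variables add an independent R² of 0.05.

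**Step 1: recall and F1 of the unchanged rule P ≥ 0.3.** Let p be the clinic proportion with P ≥ 0.3, π0 the clinic event rate, and π1 the event rate among those with P ≥ 0.3. Then:

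- prevalence = (1 − f)π0 + fπ1
- proportion above the cut, A = (1 − f)p + f
- precision = π1, which does not contain f
- recall = π1·A / prevalence
- F1 = 2·precision·recall / (precision + recall)

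For s = 1.0: p = 0.3274, π0 = 0.4207, π1 = 0.623.

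- f = 0: recall = 0.623 × 0.3274 / 0.4207 = 0.485; F1 = 0.546.
- f = 0.25: prevalence = 0.75 × 0.4207 + 0.25 × 0.623 = 0.471; A = 0.75 × 0.3274 + 0.25 = 0.496; recall = 0.623 × 0.496 / 0.471 = 0.655; F1 = 0.639.
- f = 0.5: prevalence = 0.522; A = 0.664; recall = 0.792; F1 = 0.70.

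Ranges over s = 0.8 to 1.2:

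| Flagged share | Prevalence | Precision | Recall | F1 |
|---|---|---|---|---|
| 0 | 0.40–0.43 | 0.62–0.63 | 0.44–0.51 | 0.52–0.56 |
| 25% | 0.46–0.48 | 0.62–0.63 | 0.63–0.67 | 0.62–0.65 |
| 50% | 0.51–0.53 | 0.62–0.63 | 0.78–0.80 | 0.69–0.70 |
| 100% | 0.62–0.63 | 0.62–0.63 | 1.00 | 0.76–0.77 |

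With R² from 0.10 to 0.40, the same formulas give a rise in F1 at a 25% share of between 0.06 (0.667 to 0.730; R² 0.40, s = 1.2) and 0.15 (0.400 to 0.552; R² 0.10, s = 0.8).

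**Step 2: strength of a non-Garmin benchmark.** Take P itself as the benchmark. With c the cut in SD units of P, L = φ(c)/p and v = 1 − L(L − c), the variance of P in the mixed sample relative to the clinic is

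V = (1 − f) + f·v + f(1 − f)L²,

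and the benchmark R² becomes R²V / (R²V + 1 − R²). The last term of V is the spread between flagged and unflagged recruits; it offsets the narrowing within the flagged group. For s = 1.0, L = 1.103 and v = 0.277:

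- f = 0.25: V = 0.75 + 0.069 + 0.228 = 1.05; R² goes from 0.20 to 0.207.
- f = 0.5: V = 0.5 + 0.139 + 0.304 = 0.94; R² = 0.191.
- f = 0.75: V = 0.25 + 0.208 + 0.228 = 0.69; R² = 0.146.
- f = 1: V = 0.277; R² = 0.065.

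If the flagged group is instead the top 20% to 50% of predictions, V is 0.96–1.17 at f = 0.25, 0.84–1.10 at f = 0.5 and 0.64–0.78 at f = 0.75.

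**Step 3: apparent Garmin gain (simulation, R² = 0.20).** The AUC gain from the same Garmin signal is about 0.025 at f = 0 and f = 0.25, 0.028 at 0.5, 0.036 at 0.75 and 0.05 at 1.

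**Step 4: cost of weighting back to the clinic.** Assume 20% of the clinic would be flagged. The sample proportion above the cut is a = f + (1 − f) × 0.2, and effective n = 200 / (0.2²/a + 0.8²/(1 − a)). At f = 0.5, a = 0.6 and effective n = 120. At f = 0.75, a = 0.8 and effective n = 62, so intervals are √(200/62) = 1.8 times as wide.

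**The case against.** The predicted-rise route is one of several and is not an eligibility rule, so its share may be small. Models with and without Garmin data would presumably be scored on the same participants, which makes the comparison fair for the enrolled mix; what remains is a question of transport to the clinic. The recruiting model and the non-Garmin comparator are inferred: the plan names neither, and a comparator using information beyond the recruiting prediction would be less affected. The available text also ends in section 28.1 although the contents list runs to section 35, so silence on model validation is weak evidence. These points stand, and they limit the claim to case mix and transport.

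They do not remove it. Step 1 shows recall and F1 moving at a share of a quarter, and section 26, which is available, lists neither item needed to correct for it.

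Two stronger readings are tempting. A reader might infer that selecting on the prediction must weaken the non-Garmin benchmark, roughly in proportion to the flagged share, and so flatter Garmin. The documents give no share, and Step 2 shows the effect is not proportional and can change sign: at a quarter or less the benchmark is about unchanged or slightly stronger. A reader might also infer that precision is inflated. For a fixed rule at the selection cut it is not, because flagged and unselected recruits above that cut have the same distribution of predictions. A refitted model or another cut could behave differently.

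**Conclusion.** The concern holds as one of case mix. Selecting an unstated share of youth on predicted HbA1c rise raises the prevalence of true risers and inflates recall and F1 with no improvement in the model. With an assumed benchmark R² of 0.20, F1 rises by roughly 0.1 at a 25% share and by about 0.14 to 0.17 at 50%. The performance reported for the HbA1c models would therefore not describe the clinic population.

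The effect on the Garmin comparison has no established direction. It is clearly exaggerated, with the AUC gain going from about 0.025 to between 0.036 and 0.05, only if flagged youth make up three quarters or more of the sample. Nothing in the plan rules that out, and nothing says it will happen.

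All sizes rest on the assumed accuracy, SD, cut and share, and on other recruits resembling the clinic, which event and referral recruits may not.

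**What to change.** - State in section 9.3 the prediction model, its horizon and whether 0.3 points is a minimum.
- Record the recruitment route for every youth and, where the recruiting prediction can be run, the predicted HbA1c change at the enrolment date. Do this for all youth, since some who enter by other routes will also have a high predicted rise.
- Define the non-Garmin comparator for Objective 4 and include the predicted value in it.
- Report Endpoint 7 for HbA1c with and without Garmin variables, separately for flagged and other recruits. Add AUC or R-squared, which do not depend directly on prevalence, and calibration. Both still respond to the spread of predictions, so they complement the split by route and do not replace it.
- Show a result weighted to the clinic's distribution of predicted change as a sensitivity analysis only.

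**Cost.** One REDCap field for route, one prediction run per youth and extra tables; recruitment and care do not change. The strata are smaller than 200. The weighted result also needs the clinic-wide distribution of predictions, and it loses substantial effective sample size if flagged recruits dominate (Step 4).

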11.0 Additional Study Activities NA Blood and Other Specimen Collection: NA

12.0 Follow-up

After the V1D1 visit, physical activity information will be collected from the participant trackers via the Garmin Connect app and uploaded into storage via the Garmin Health API connection developed by Children's Mercy Research Informatics. If the participant experiences any issues with tracker activation or use, additional study visits will be scheduled at Visit 2, Visit 3 and Visit 4 (approximately Day 14, 28, or 52).

Participants will have information collected from the devices until 365 (+/- 30 days) days following start of study, at which point they will have one more SOC clinic visit, complete surveys, and then will have completed the study requirements. There will not be any research follow up after this point, and if the participants elect to discontinue from the study, there will be no follow up. When participants complete the study requirements or elect to discontinue, they will be marked as such in the RedCap database of study participants. We will ask the patients if they are willing to complete the surveys prior to discontinuing the study.

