If the subject wears the tracker for >8 hours between 9 AM and 9 PM, the day is used in the weighing calculation (Grimes et al., 2022). Clinical data will be collected from the medical record and coded (labeled with the study ID to minimize use of personal data). Also, self-reported personal health will be collected from the CMH-approved vendor software to which they upload their self-management device data. Baseline and end of study surveys including International Physical Activity Questionnaire (IPAQ), the Hypoglycemic Fear Scale II (HFS-II) for participants, and Hypoglycemic Fear Scale for parents (HFS-P) will be collected from participants/ parents. Surveys will be given to participants based on their ages and the ages surveys are validated for.

Table of Events:

	Pre-screening (Pre-consent)	Visit 1 Day 1 app x.	Visit 2 ^a Day 14 appx. (PRN)	Visit 3 ^a Day 28 appx. (PRN)	Visit 4 ^a Day 56 appx. (PRN)	Visit 5 Day 180 appx.	Visit 6 Day 365 appx.	Unscheduled Visit
EMR Review Eligibility	X							
Verbal Consent		X						
Demographics		X						
Clinical history ^b		X					X	
Send Garmin tracker		X						
Surveys ^c		X				X	X	
Mid-Study Check-In Survey						X		
Garmin Troubleshooting Visits			X	X	X			

- a. Additional virtual or in person visits may be scheduled at Visit 2, Visit 3, and Visit 4 as needed for device troubleshooting and additional education, depending on the needs of the subjects
- b. A1c will be drawn SOC as a part of the clinical history, in the absence of A1c results, GMI will be deduced from CGM data
- c. The IPAQ (for >15 YO) and HFS-P/HFS-II (HFS-II child for 11-18 Y.O., HFS-II adult for >18 YO)

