25.0 Withdrawal of Participants*

Participants may withdraw from the study at any time at their own request, or they may be withdrawn at any time at the discretion of the investigator. Reasons for withdrawal may include:

- Participant no longer wants to participate in study visits/procedures/processes.
- Participant's clinical care deciding it is not in their best interest to continue participation
- Participant stops providing information and cannot be reached by the research staff. For example, lost to follow up after three active attempts to contact participant (not including automated alerts, for example the automatic texts triggered when watches are inactive)

If a participant is withdrawn or lost to follow up, this will be documented appropriately in the REDCap database developed for research documentation since this study may not be recorded in the medical record per CMH policy.

All data collected prior to the participant withdrawal will be retained.

DATA MANAGEMENT

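### Sections 12 and 25 do not separate lapsed wear or contact from withdrawn permission, so late outcomes that need no research contact can be lost

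*Combined protocol and SAP*

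**What the plan says.** Section 12.0 has an ending for completers and one for early leavers. For completers, "Participants will have information collected from the devices until 365 (+/- 30 days) days following start of study"; a last standard-care visit and surveys follow, and then "There will not be any research follow up after this point". For early leavers, "if the participants elect to discontinue from the study, there will be no follow up", though they are asked for surveys before they go.

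Section 25.0 allows withdrawal at the participant's request or at the investigator's discretion. One possible reason is "Participant stops providing information and cannot be reached by the research staff", with three active contact attempts as the example. Status is recorded: "If a participant is withdrawn or lost to follow up, this will be documented appropriately in the REDCap database". The only data rule is "All data collected prior to the participant withdrawal will be retained".

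Several outcomes do not depend on research contact. Section 4.0 takes HbA1c from the electronic medical record, "obtained via standard care (binned as 46-135 days, 136-225 days, 226-305 days, and 306-410 days". Section 5.0, note b to the Table of Events, adds that "in the absence of A1c results, GMI will be deduced from CGM data". Section 26.0 has CGM data download automatically from a linked personal account. Section 4.0 counts DKA hospital admissions in windows of 0-180 and 181-365 ± 30 days. It does not name their source, but the medical record is the natural one.

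Section 21.4 covers participants who turn 18. Collection pauses while adult consent is sought, and the participant's entry is deleted if a third contact fails.

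**The concern.** A participant may stop wearing the watch, stop answering calls, or withdraw permission to use their records. Only the last of these is a reason to stop reading a clinic HbA1c or a hospital admission. Sections 12.0 and 25.0 attach no separate data rule to each. The literal rule for elective leavers is a full stop, and for other exits the only assurance concerns data already collected.

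Primary objectives 2 to 4 run to 365 ± 30 days, so the outcomes exposed are primary. Losing them costs precision. If people with worsening control are more likely to leave, late-window DKA rates and analyses of early activity against later outcomes may also be biased.

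**Working it through.** **1. Which outcomes fall after exit.** The windows are from Section 4.0. An exit at Day 180 is taken as a worked case.

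- HbA1c 136-225: 225 - 136 + 1 = 90 days, of which 181-225 = 45 fall after exit.
- HbA1c 226-305: 80 days, all after exit.
- HbA1c 306-410: 105 days, all after exit.
- DKA 181-365 ± 30: all after exit. DKA 0-180 is unaffected.
- 14-day Time in Range at 365 days: after exit.

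**2. Precision.** The youth enrollment goal is 200 (Section 8.0). The documents give no attrition rate, so 10-30% is assumed, leaving 180 to 140 in the late windows.

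- Standard error inflation: sqrt(200/180) = 1.054; sqrt(200/140) = 1.195.
- Smallest correlation detectable with 80% power, two-sided 5% (assumed): r = tanh[(1.960 + 0.842)/sqrt(n - 3)]. This gives 0.197 at n = 200, 0.208 at 180, 0.220 at 160 and 0.235 at 140.

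**3. Bias in an activity-outcome slope.** Assume bivariate normality, with leavers being the top share d on an index correlated rx with activity and ry with worsening outcome. With c = z(1-d) and L = φ(c)/(1-d), let δ = cL + L². For d = 0.1, 0.2, 0.3, δ = 0.288, 0.417, 0.507. The slope among stayers, relative to the full cohort, is [(ρ - rx·ry·δ)/(1 - rx²·δ)]/ρ. Take ρ = -0.2 for activity against HbA1c change.

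- Leaving related to both (rx = -0.3, ry = 0.3): 0.894, 0.844, 0.809. At d = 0.1: (-0.2 + 0.09 × 0.288)/(1 - 0.09 × 0.288) = -0.1741/0.9741 = -0.1787, and -0.1787/-0.2 = 0.894.
- Leaving driven by outcome only (ry = 0.3, rx = -0.2 × 0.3 = -0.06): 0.975, 0.964, 0.956.
- Leaving driven by activity only, or by neither: 1.000.

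For Time in Range, where higher is better, ρ and ry both change sign and the ratios are the same.

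**4. DKA rate in the 181-365 window.** If a share d exits at Day 180 with k times the stayers' risk, and none of their later events are read, observed/full-cohort = 1/[(1-d) + dk].

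- d = 0.1, k = 1.5: 1/1.05 = 0.952.
- d = 0.2, k = 2: 1/1.20 = 0.833.
- d = 0.3, k = 3: 1/1.60 = 0.625.
- k = 1: 1.000 at any d.

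**5. Retention at 18.** Section 25.0 keeps everything gathered before withdrawal and states no exception. Section 21.4 deletes the entry after a third failed contact. An 18-year-old who cannot be reached could fall under both. If ages 8-21 (14 single years) are evenly spread, 200/14 = 14.3 youth turn 18 per year, or 14.3 × 395/365.25 = 15.4 over the longest participation. The share who would not respond is unknown.

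**The case against.** The strongest reply is that Section 12.0 already states a rule for people who elect to discontinue, and ending follow-up when someone leaves respects their choice. This stands. A reader might infer that the protocol is silent, but for this group it is not; the issue is how far the rule reaches. Section 12.0 speaks of research follow-up for completers and of follow-up without that qualifier for leavers, so a narrower meaning is possible, but the plain reading is a full stop. The real gap concerns participants who are unreachable or withdrawn by the investigator.

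Section 25.0 also lists its withdrawal reasons separately, and it does not list stopping wear as an exit: inactive watches trigger automatic texts. This stands too, but no data rule is attached to any of these situations.

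A reader might see a conflict between the last HbA1c bin, ending at Day 410, and participation ending by Day 395. There is none. Every possible final visit day, 335 to 395, lies within 306-410, and an analysis bin may be wider than the visit window.

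A reader might also call Section 21.4 an error, or conclude that data must be kept after failed reconsent. The documents support neither. The change log shows that the section was revised deliberately to address reconsent, and retention is a consent decision. Only the missing cross-reference remains.

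Finally, the attrition shares, correlations and risk ratios are assumptions. HbA1c change is named only as a machine-learning target (objective 4), not in the association objectives. Leavers supply no later activity data, so record reading helps only analyses that use activity recorded before exit. The information letter and addenda are not in the supplied text, which ends at Section 28.1, so a rule elsewhere cannot be excluded.

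**Conclusion.** The concern holds as a design choice that should be changed. Followed literally, Sections 12.0 and 25.0 give up late-window HbA1c, DKA and Time in Range for people whose records remain readable. The windows affected follow from the documents; the size of the damage does not. Under 10-30% attrition, the precision loss is modest (standard errors up 5-20%). The slope falls to 0.89-0.81 of its full-cohort value only if leaving is tied to both activity and outcome at the assumed strengths. It is 0.975-0.956 if leaving is tied to outcome alone, and unchanged if tied to activity alone or to neither. The DKA ratios of 0.95 to 0.63 also require that all leavers exit at Day 180 and that none of their later events are read. The difference between Sections 21.4 and 25.0 is a smaller, separate matter of reconciliation.

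**What to change.** In Sections 12.0 and 25.0, define three states: (a) stopped wearing the device; (b) unreachable, or withdrawn by the investigator; (c) permission withdrawn. For (a) and (b), continue extracting HbA1c and DKA admissions from the medical record to the end of the endpoint windows in Section 4.0, and CGM while the account stays linked, where the information letter and the IRB permit. For (c), stop. Participants who elect to discontinue could be asked which state applies at the contact where exit surveys are already requested.

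Add exit date and reason to the REDCap status, and report the number of leavers by outcome window. Separately, add a cross-reference or a stated exception so that Sections 21.4 and 25.0 agree on data held when adult consent is not obtained, leaving the choice to the IRB.

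The cost is protocol wording, possibly information-letter wording, and IRB review, with no new visits. Device and survey data after exit are not recovered, HbA1c still depends on clinic attendance, and CGM on continued use and sharing.
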